6.7.1.1. Suggestions for Rash Management

Papulopustular (acneiform) rash is the most common rash seen with EGFR inhibitors, and is typically seen in the first few weeks of treatment. It usually peaks at Weeks 4 to 6 and decreases in severity between Weeks 6 and 8. Post-inflammatory skin changes can last for months, so prevention and reactive treatment are important.

Suggestions for the management of skin rash are provided in Table 4.

Table 4: Suggestions for Skin Rash

Stage	Suggested Treatment for Skin Rash
Preventative Treatment	 Subject education prior to starting treatment on what to expect Gentle cleansing of skin using mild soap products Use of moisturizer twice daily making sure to include hands, feet, and nails Avoid sun when possible and use of sunscreen SPF 30 or higher (preferably titanium dioxide or zinc oxide) Use UVA ocular protection (ie, sunglasses with UVA filtering) when outside Hypoallergenic makeup when possible
Once Rash Appears ^a	 Ongoing use of treatments from preventative treatments above Mild (<10% BSA involved, without pruritus or tenderness) Topical steroids (refer to Appendix 3 for a steroid potency chart that categorizes brand- name topical steroid medications) For face, use medium potency
	 For body, use strong potency Note: As soon as rash improves the lowest strength steroid that controls rash should be used, especially on the face Moderate (10%–30% BSA involved, ± pruritus/tenderness; limiting instrumental ADLs and causing psychosocial impact) Topical steroids For face, use strong potency For body, use very strong potency
	 Note: As soon as rash improves the lowest strength steroid that controls rash should be used, especially on the face Systemic Treatment Doxycycline 100 mg BID (less renal toxic than minocycline, but can cause photosensitivity) Severe (> 30% BSA involved, limiting ADLs) Refer to dermatology Topical steroids All areas very strong potency Note: As soon as rash improves the lowest strength steroid that
	controls rash should be used, especially on the face Systemic treatment Doxycycline 100 mg BID Oral steroids: prednisolone 10 mg QD for 1 week or equivalent

Once	Rash
Reap	pears

- Over the course of treatment rash may come and go
 - Hydrocortisone 1% cream with moisturizer and sunscreen BID, in combination with doxycycline 100 mg BID
 - May need to follow guidelines above if rash worsens

If unacceptable rash recurs on reintroduction of tesevatinib at the same dose, then discontinuation of tesevatinib should be discussed with the Medical Monitor.

Abbreviations: ADL, activity of daily living; BID, twice daily; BSA, body surface area; QD, once daily; SPF, sun protection factor; UVA, ultraviolet A

a See Appendix 3 for steroid potency chart.

Source: Lacouture, 2011⁹, Kiyohara 2013¹⁰, www.psoriasis.org

QT Interval Prolongation

Risk factors for occurrence of arrhythmia include hypokalemia, hypomagnesemia, bradycardia, and concurrent use of multiple medications that prolong the QTcF interval. In vivo observations of QTcF prolongation in association with use of tesevatinib have been observed, including severe QTcF prolongation. However, the lack of a clearly discernible pattern to such occurrence makes prediction of individual subject risk difficult. Therefore, the following are recommended:

- Study drug should be administered to subjects who have normal serum potassium and serum magnesium levels.
- Study drug should not be administered to subjects with pathologic bradycardia.
- Medications with potential for QTcF prolongation should not be used concurrently or started within 24 hours of study drug administration.

Subjects should be carefully monitored for symptoms of arrhythmia (ie, dyspnea, chest pain or tightness, palpitations, dizziness) and for episodes of syncope. An ECG should be obtained if these symptoms occur. In addition, serum potassium and magnesium must be maintained within the normal range¹¹ and may require additional monitoring or adjustment if subjects develop diarrhea.

6.7.1.2. Response to QTcF Interval Prolongation

The following guidelines should be used in the management of QTcF prolongation. Subjects will have ECGs performed as outlined in Table 2. If the average QTcF interval (from 3 consecutive ECGs taken with an interval of at least 1-2 minutes within 30 minutes) increases to > 60 msec above the highest average predose value (average of Day 1 predose and screening values) or to the level of ≥ 480 msec according to local site analysis:

- Hold study drug until central read is confirmed.
- Check electrolytes, especially magnesium and potassium; correct abnormalities as clinically indicated.
- Manage as clinically indicated with cardiology consultation as needed.
- Contact the Medical Monitor to discuss additional monitoring.

If results are confirmed by the central reader, the subject may be removed from the study after discussion with the Medical Monitor. If the subject continues in the study, appropriate management and ECG follow-up should be discussed with the Medical Monitor.

Elevated Amylase

If subjects develop an elevated serum amylase during the study that is $> 2.0 \times ULN$, then additional evaluations should be performed. These should include evaluating serum lipase, amylase isoenzymes, and fasting triglycerides as well as obtaining history regarding symptoms of pancreatitis, symptoms of dry mouth, and use of alcohol. The subject should have a drug holiday for 28 days, with amylase measured at the end of the drug holiday. If the amylase is back to the baseline value after the end of the drug holiday, study drug may be restarted, and amylase measured approximately 14 days later, and then at the start of each cycle of study drug administration. If results continue to be abnormal, the subject will be removed from study. If an elevated serum amylase that is $> 2.0 \times ULN$ occurs a second time, the subject will be removed from the study.

Elevated Creatinine Phosphokinase

If subjects develop an elevated serum CPK during the study that is $> 2.0 \times$ ULN, additional evaluations should be performed. These should include evaluating serum CPK isoenzymes as well as obtaining history regarding muscle-related symptoms or strenuous or prolonged exercise.

Pulmonary Toxicity

If subjects experience an acute onset of new and/or progressive, unexplained pulmonary symptoms such as dyspnea, cough, and fever, study drug should be held while subjects are evaluated. If interstitial lung disease is diagnosed, study drug should be discontinued and treatment administered as necessary.

Hepatotoxicity

Rare cases of hepatic failure have been reported. Confounding factors have included pre-existing liver disease or concomitant hepatotoxic medications. Liver function test abnormalities (including elevated ALT, AST, and bilirubin) have been observed in clinical studies with tesevatinib. Interruption of study drug should be considered in subjects developing liver function abnormality $> 3 \times ULN$.

Management guidelines for liver function abnormalities are provided in Table 5.

Table 5: Management Guidelines for Liver Function Abnormalities

Liver Function Abnormality	Occurrence	Action
Hyperbilirubinemia		
$2.5 - < 3 \times ULN$	1 st	Hold dose; resume dosing when recovered or reduced to mild intensity.
	2 nd	Off study.
> 3 × ULN	1 st	Off study.
AST/ALT elevations		
2.5 – < 3 × ULN	1 st	Hold dose; resume dosing when recovered or reduced to mild intensity.
	2 nd	Hold dose and discuss management with Medical Monitor.
> 3 × ULN	1 st	Hold dose and discuss management with Medical Monitor.
	2 nd	Off study.

Abbreviations: ALT, alanine aminotransferase; AST, aspartate aminotransferase; ULN, upper limit of normal

Pericardial Effusion

Pericardial effusions have been seen in oncology studies with tesevatinib. In addition, 1 subject with ADPKD receiving 50 mg tesevatinib daily developed a trace pericardial effusion. The guidelines outlined below should be followed in the event that a subject develops a pericardial effusion while receiving tesevatinib.

For an asymptomatic pericardial effusion that is at least moderate in size, a follow-up echocardiogram should be performed within 1–3 months to monitor for progression. Results of the additional echocardiogram should be discussed with the Medical Monitor to determine subject management.

Subjects should be monitored for signs and symptoms of cardiac tamponade. In addition to the monthly to bimonthly physical exam of blood pressure, pulse, respiration, weight, heart, and lung, physical exam should also asses for tachycardia, dyspnea, neck vein distension, and edema.

Adrenal Insufficiency

One case of adrenal insufficiency has been reported in an oncology subject receiving tesevatinib. Subjects should be monitored for signs or symptoms of adrenal insufficiency and the Medical Monitor immediately notified if symptoms are observed.

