6.7. Warnings, Precautions, and Management

Adverse events that have been associated with tesevatinib include the following: diarrhea, skin rash, QTcF prolongation, hepatotoxicity, and pulmonary toxicity. Study drug may be held for up to 28 days at the discretion of the Investigator (unless otherwise specified below), except during the first 28 days of dosing (Early Treatment Period).

Diarrhea

Diarrhea should be managed according to accepted practice (eg, with loperamide). Subjects with severe diarrhea who are unresponsive to loperamide or who become dehydrated may require interruption of study drug until resolution to ≤ mild in intensity. If subjects are in the monthly treatment period, drug may be held for up to 28 days. If severe diarrhea occurs during the 28-day Early Treatment Period, subjects must be discontinued from the study. In the event of severe or persistent diarrhea, nausea, anorexia, or vomiting associated with dehydration, study drug should be discontinued, and appropriate measures should be taken to rehydrate the subject intensively via intravenous administrations. Subjects should be advised to contact the investigator immediately if they develop significant diarrhea; should this occur, an electrolyte panel, including magnesium and potassium, and ECG should be performed.

Skin Rash

Skin rash should be managed according to locally accepted clinical recommendations. Study drug may be held up to 28 days at the discretion of the investigator and after discussion with the Medical Monitor. The following guidelines may be considered.

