Electrocardiograms will be performed with the subject in a supine position having rested in this position for at least 5 minutes before each reading. Triplicates should be obtained, with an interval of 1-2 minutes between ECGs.

During the study, all ECGs will be digitally analyzed by a validated central ECG vendor. Additional details on collection of ECGs will be provided in a separate manual.

The QT interval will be corrected using Fridericia's formula, adapted from Fridericia, 1920 12:

$$QT_F = \frac{QT}{RR^{1/3}}$$

All subjects must demonstrate an average screening QTcF value of \leq 450 msec by central digital analysis in order to be enrolled in the study. During the study, immediate clinical management of subjects will be based on results of machine-read ECGs at the sites. However, the central digital analysis will prevail as it becomes available. In addition, the central digital analysis will be used for any AE and SAE documentation.

An increase in QTcF interval (by central digital analysis) to a value > 60 msec above baseline or to the level of ≥ 480 msec requires further monitoring and, after collection of a PK blood sample and discussion with the Medical Monitor on appropriate management, the subject may be removed from the trial (see guidelines in Section 6.7.1.2).

Abnormalities in the ECG that lead to a change in subject management (eg, requirement for additional medication or monitoring) or result in clinical signs and symptoms are considered clinically significant for the purposes of this study and will be recorded on the AE eCRF. If ECG abnormalities meet criteria defining them as serious, they must be reported as an SAE (see Section 8.2.3).

Echocardiogram

Echocardiograms for determination of ejection fraction and evaluation of pericardial effusion and cardiac valve function will be collected at the time points specified in Table 2.

Ocular Monitoring

Ocular monitoring will be performed at the time points specified in Table 2. Ocular monitoring will include an assessment of best corrected distance visual acuity, fundoscopic exam with non-dilated pupils, slit lamp photography of the iris, non-mydriatic photography of retina within the arcade, and optical coherence tomography of the optic nerve head and macula.

Clinical Laboratory Evaluations

A central laboratory will perform clinical laboratory evaluations.

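### A QTcF crossing seen only on the central ECG read, the read that prevails, carries no required dose hold before the Medical Monitor discussion

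*Protocol*

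**What the plan says.** Protocol Section 6.7.1.2 sets the response to QTcF prolongation. The trigger is an average QTcF more than 60 msec above the predose reference value, "or to the level of ≥ 480 msec according to local site analysis". The site must then "Hold study drug until central read is confirmed", check electrolytes, manage as clinically indicated, and contact the Medical Monitor about additional monitoring. The next step reads: "If results are confirmed by the central reader, the subject may be removed from the study after discussion with the Medical Monitor". If the subject stays in, management and ECG follow-up are to be discussed with the Medical Monitor. Table 2 footnote f also refers the site to this section on the basis of the local read.

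The Electrocardiogram text of Section 7.5 deals with the two reads. Immediate management uses the site's machine read. "However, the central digital analysis will prevail as it becomes available". A crossing of the same size by central analysis calls for further monitoring. The text then says that "after collection of a PK blood sample and discussion with the Medical Monitor on appropriate management, the subject may be removed from the trial", with a reference back to 6.7.1.2. No hold is stated there. On ECG logistics it adds: "Additional details on collection of ECGs will be provided in a separate manual".

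Section 6.7 gives the investigator a general discretionary hold of up to 28 days, with the qualifier "unless otherwise specified below), except during the first 28 days of dosing (Early Treatment Period". For raised AST/ALT, Table 5 pairs the two steps in one instruction: "Hold dose and discuss management with Medical Monitor".

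**The concern.** Followed as written, the provisional read stops dosing and the authoritative read does not. The protocol expects the two reads to differ at times, since it says which one prevails. The central result also comes after the local one, by which time the subject may be at home taking a tablet each morning (Section 6.2). The site then has a confirmed threshold value and a duty to discuss it, but no instruction on the next dose.

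QTcF prolongation is a named risk of tesevatinib. The QT Interval Prolongation text of Section 6.7 says severe cases have been observed and that individual risk is hard to predict. Moderate prolongation in 2 subjects at 100 mg led to the choice of 50 mg (Section 1.3). The terminal half-life is 50 to 92 hours (Section 1.2.1.3), so a dose taken during the gap is not cleared quickly.

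**Working it through.** The plan states no figure on this point, so the check sets the provisions side by side.

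**Inputs.** Section 6.7.1.2 (trigger, hold and its end point, steps after confirmation); Table 2 footnote f (routing); Section 7.5, Electrocardiogram (central read prevails, actions on a central crossing); Section 6.7 opening paragraph (general hold and its exclusion).

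**Hold coverage by case.**

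| Case | QTcF hold in 6.7.1.2 | General hold, Days 1 to 28 | General hold, Day 29 on |
|---|---|---|---|
| A. Local crossing, central read pending | Required | Not needed | Not needed |
| B. Local crossing, centrally confirmed, Medical Monitor decision pending | Ambiguous: worded to end at confirmation, but nothing says to resume | Excluded | Discretionary |
| C. Crossing on the central read only | None required | Excluded | Discretionary |

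**Case C** is the gap. Section 7.5 covers it with monitoring, a PK sample and a discussion, then refers to 6.7.1.2. The hold found there starts on a local crossing, which has not happened, and ends when the central read is confirmed, which has already happened. Neither its start nor its end fits the case.

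**Case B** is a wording ambiguity. The Medical Monitor has already been contacted while drug is held, so any gap is likely short.

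**Other provisions checked.** Section 5.2 and Appendix 2 contain QT-related holds, but for concomitant QT-prolonging drugs, not for an observed crossing. SAP Section 3.13.4 only tabulates QTcF categories.

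**Where the scheduled ECGs fall** (Table 2, footnotes b and f), counting on-treatment time points:
- Day 1 at 1, 4 and 8 hours: 3
- Day 14 predose and at 1, 4 and 8 hours: 4
- Day 28 predose: 1
- Months 2 to 12: 11
- Months 14 to 24, every 2 months: 6
- Total: 3 + 4 + 1 + 11 + 6 = 25

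Days 1 and 14 supply 3 + 4 = 7, and 7/25 = 28%. With Day 28 it is 8/25 = 32%. All 3 + 3 = 6 time points with a stated post-dose hour fall on Days 1 and 14, inside the period when the general hold is excluded. This shows where ECG monitoring is densest. It does not measure the gap, which also needs a crossing and a disagreement between the two reads.

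**Length of the gap.** Dosing is once daily, so a gap of d days means d doses of 50 mg. The documents give no central turnaround time, no time limit for the discussion and no local-central agreement figure, so d and the number of subjects cannot be stated.

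**The case against.** The strongest reply is that the protocol already implies a hold. The central value replaces the local one as the basis for management, a discussion is mandatory, and Section 7.5 refers to the 6.7.1.2 guidelines, which include both a hold and management as clinically indicated. The investigator or sponsor may also withdraw a subject for safety at any time (Section 4.3). A careful site would probably stop dosing. All of this is true and limits the seriousness of the point. But none of it is a hold instruction, and the cross-reference leads to a hold whose trigger is the local read.

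Two stronger readings are tempting, and the documents do not support them.

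- A reader might infer that QTcF holds are barred in Days 1 to 28. They are not. Section 6.7 excludes only the general discretionary hold and makes room for holds specified below it. The hold in 6.7.1.2 has no early-period limit.
- A reader might infer that a local crossing, once centrally confirmed, sends the subject back to dosing. No sentence says so. The end point of the hold can be read as marking where the next paragraph takes over, with removal or management settled with the Medical Monitor.

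The separate ECG manual may contain a central alert procedure. The protocol describes it as covering collection, and its content is not known here.

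**Conclusion.** The point holds for a crossing seen only on the central read: no required hold covers dosing between that result and the Medical Monitor discussion. From Day 29 a discretionary hold is available. In Days 1 to 28 it is not, and the only written QTcF hold is tied to the local read. The missing continuation of the hold after central confirmation of a local crossing is a secondary ambiguity.

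It would be wrong to conclude that central-read crossings go unmanaged, or to size the problem by the number of early ECG readings. Monitoring, a PK sample and a discussion are required, and the gap is confined to the doses taken before that discussion. Its length and frequency cannot be stated from the documents. The conclusion assumes that the two reads can disagree, which the protocol itself provides for, and that the ECG manual contains no dosing rule. It relies on no rate of prolongation at 50 mg. This is a cheap improvement to a safety rule; it does not undermine the trial's design.

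**What to change.** Add to Section 6.7.1.2: *If the average QTcF is ≥ 480 msec or > 60 msec above the predose reference value by central analysis, whether or not the local read crossed, hold study drug (or continue the hold) until the Medical Monitor discussion is complete and a dosing decision is recorded. This applies at any time, including Days 1 to 28.*

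In Table 2 footnote f, widen the trigger from the local ECG read to the local or central ECG read.

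The cost is two sentences and one phrase. All ECGs already go to the central vendor and the discussion is already required, so no new procedure is needed. The downside is a few missed doses in subjects who are then allowed to resume.

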7. STUDY PROCEDURES

7.1. Study Schedule

The schedule of assessments for this study is provided in Table 2.

All screening assessments are to be performed within 28 days prior to the first dose of study drug, unless otherwise specified. Study eligibility will be based on satisfying all of the study inclusion and exclusion criteria. Day 1 is defined as the date the subject takes the first dose of study drug.

A screen failure is a subject who has given informed consent and failed to meet the inclusion and/or meet at least 1 of the exclusion criteria and has not been randomized or administered investigational product(s) as defined by the protocol.

7.2. Informed Consent Process

The subject will be given a verbal explanation of the study, including information about the study drug and the study procedures, and will have all questions adequately addressed. The subject must sign and date a consent form that has been approved by the IRB before the screening procedures are initiated. All subjects will be given a copy of the signed and dated informed consent form.

7.3. Demographics and Medical History

A complete medical history will be taken. Information to be documented includes demographic information, prior medical illnesses and conditions (including PKD genotype, if available), and surgical procedures.

7.4. Randomization

Each subject who completes the study screening assessments, meets all eligibility criteria will be assigned a unique identification number and will receive the corresponding treatment according to a randomization scheme generated by the IVRS/IWRS vendor. The randomization schedule will be prepared by the IVRS/IWRS vendor using a validated program. The IVRS/IWRS will assign a randomization number to subjects that will be used to link the subject to a treatment group and will specify a unique medication number for the study drug to be dispensed to the subject. Randomized subjects who terminate their study participation for any reason, regardless of whether study treatment was taken or not, will retain their randomization number. IVRS/IWRS personnel not involved with any of the protocol operations will prepare the randomization schedule.

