Informed consent	>					
Medical and PKD history (include genotype, if available)	*					
Physical examination ^d (including weight)	~	~	~	~	~	~
Vital signs ^e	~	~	~	~	~	~
Supine 12-lead ECG ^f	~	~	~	~	~	~
Clinical laboratory tests ^g	~	~	~	~	~	~
Ocular evaluation ^h	>				•	>
Echocardiogram ⁱ	>			~	~	~
Pregnancy test ^j	>	~		~	~	~
MRI ^k	•				(every 6 months beginning at Month 12)	•
Randomization		~				
Study drug/placebo dispensed		~	~	*	~	>
Record adverse events	>	~	~	~	~	~
Record concomitant medication	>	~	~	*	•	>
Drug compliance/collection ¹		~	~	~	~	~

Abbreviations: ECG, electrocardiogram; MRI, magnetic resonance imaging; PKD, polycystic kidney disease; QTc(F), QT interval corrected for heart rate using Fridericia's formula; TSH, thyroid stimulating hormone

- a. Screening evaluations may be combined with Day 1 pre-treatment laboratory evaluations if both are done within 4 days before first dose of study drug. Screening MRI and ocular assessments may be performed up to 6 weeks prior to Day 1.
- b Follow-up treatment period visits to be performed monthly (every 28 ± 1 day). For those subjects continuing on study beyond 12 months, visits will occur every 2 months ± 3 days between Months 12 and 24.
- c. The End-of-study visit is to be performed 30 days (± 3 days) after last dose of study drug.
- d. A complete physical examination is to be done at the Screening and End-of-study visits. Height will only be measured at Screening. Symptom-driven physical examinations will be performed on Days 1, 14, 28, every 28 days from Months 2 to 12, and every 2 months from Months 12 to 24. See Section 7.5.1 for a description of the body systems and evaluations to be performed at each visit (eg, cardiac tamponade, ocular toxicity and xerostomia assessments).
- e. Vital sign measurements will include sitting blood pressure, heart rate, respiratory rate, and oral or tympanic temperature. On Day 1, measurements should be performed predose and 1 and 4 hours postdose. See Section 7.5.2 for details on vital signs measurement.

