- k. Screening MRI will be performed after informed consent form has been signed and prior to other screening assessments. Magnetic resonance imaging will be performed at Month 12, 18, and 24, and at the End-of-study visit
- 1. Subject diaries will be dispensed on Day 1 and reviewed/collected at each visit.

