Adverse events of special interest as of the data cutoff of October 2016 are described below.

Diarrhea and Rash

Diarrhea and rash were both expected as they are a class effect of all EGFR inhibitors.

At 150 mg QD, 3 of 5 patients had moderate rash occurring during the first 28 days, the event led to study discontinuation in 2 of the patients. The tolerability of intermittent dosing schedules using 150 mg (Monday, Wednesday, and Friday or Monday and Thursday) was

^a Includes 9 subjects from Cohort 1 and 15 subjects who were enrolled in the Phase 2a portion of the study.

^b One subject did not have a baseline TKV value.

improved over 150 mg QD, but 1 case of severe rash occurred in a patient receiving 150 mg on Monday and Thursday. While rash at the 150 mg dose level did not meet strict safety criteria for defining the maximum tolerated dose (MTD), this dose level was considered intolerable for long-term administration in this population. Therefore, the MTD for daily dosing was determined to be 100 mg daily.

Creatine Phosphokinase Elevations

There were 41 subjects with elevations of CPK above the normal range in Study KD019-101. Ten subjects experienced moderate CPK elevation (> 2.5 × upper limit of normal [ULN] – 5.0 × ULN), and 7 subjects experienced severe CPK elevation (> 5.0 × ULN). Quantitative whole body radiography in rats indicates relatively low accumulation of tesevatinib in skeletal muscle. In Study KD019-101, muscle AEs correlated poorly with CPK levels. While elevations of CPK commonly occur with exercise, the lack of a control group in Study KD019-101 makes it difficult to fully evaluate the relationship between tesevatinib and CPK elevations.

Amylase Elevations

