3. STUDY DESIGN

This is a Phase 2b, multicenter, double-blind, randomized, parallel group study to evaluate the change from baseline in htTKV as measured by MRI in subjects with ADPKD treated with tesevatinib or placebo. Male and female subjects with ADPKD, 18 to 60 years of age and with an eGFR \geq 30 mL/min/1.73 m² and \leq 80 mL/min/1.73 m² will be enrolled. Up to 100 male and female subjects will be randomized 1:1 to receive 50 mg of tesevatinib QD or placebo. The study will be conducted at approximately 25-30 sites in the United States.

Subjects will be screened up to 28 days before initiation of treatment with tesevatinib or placebo (certain screening assessments may be conducted up to 42 days prior to dosing). Screening assessments will include medical and PKD history, physical examination, vital signs, electrocardiograms (ECGs), clinical laboratory evaluation (including hematology, serum chemistry, coagulation, thyroid stimulating hormone, urinalysis, and pregnancy), ocular examination, echocardiogram, and MRI. Calculation of htTKV at screening for eligibility determination may be performed by a local radiologist.

Starting on Day 1, subjects will receive 50 mg QD of tesevatinib or placebo for up to 24 months. During the Early Treatment Period (Days 1 to 28), subjects will report to the study site on Days 1, 14, and 28; subjects will be followed every 28 days from Months 2 to 12 and every other month from Months 12 to 24. Safety assessments will be performed at regular intervals throughout the study and will include physical examinations, vital signs, ECGs, clinical laboratory evaluations, ocular examination and echocardiograms. Magnetic resonance imaging to determine the change from baseline in htTKV will be performed at Months 12, 18, and 24. Entry into the study will be based on local MRI readings, but central MRI readings and htTKV calculation will be performed at baseline and during the study.

All subjects will undergo an end-of-study evaluation approximately 30 days after the last dose of study drug.

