9.5. Selection of Subjects to be Included in the Analyses

The following populations will be used in this study:

• The Modified Intent-To-Treat (mITT) population: as all randomized subjects who received at least 1 dose of study drug.

• The Efficacy Population: all subjects in the mITT population who complete at least 12 months of tesevatinib or placebo treatment and have a centrally read MRI at baseline and after 12 months of treatment.

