3.3 Analysis Populations

The following are the set of analysis populations.

Screened Population: All subjects who sign the Informed consent form (ICF) will be included in the Screened Population.

Safety Population: The Safety Population is defined as all subjects who receive at least 1 dose of study medication. Subjects will be analyzed according to the study drug they actually received.

Intent-to-treat (ITT) Population: The ITT population is defined as all randomized subjects. Subjects will be analyzed according to the study medication to which they were randomized.

Modified Intent-to-treat (mITT) Population: The mITT Population is defined as all subjects who receive at least 1 dose of study medication. The mITT Population will be used for tables of demography and baseline characteristics. Subjects will be analyzed according to the study medication to which they were randomized.

Efficacy Population: The Efficacy Population is defined as all subjects in the mITT population who complete at least 12 months of tesevatinib or placebo treatment and have a centrally read MRI at baseline and after 12 months of treatment. Subjects will be analyzed according to the study drug they actually received. This will be the primary population for efficacy analyses.

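### Randomisation does not wait for confirmation that the one scheduled pre-dose MRI can be read centrally, although the primary htTKV analysis requires a central baseline reading (small effect, inexpensive to close).

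*Protocol*

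**What the plan says.** **Entry and randomisation.** Protocol Section 3 says: "Entry into the study will be based on local MRI readings, but central MRI readings and htTKV calculation will be performed at baseline". It also says: "Calculation of htTKV at screening for eligibility determination may be performed by a local radiologist". Section 7.4 sets the condition for randomisation: "Each subject who completes the study screening assessments, meets all eligibility criteria will be assigned a unique identification number". It names no image-quality or central-reading step, and Section 7.6 on MRI adds none.

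**Scan schedule.** Table 2 has one pre-dose MRI, at Screening; the next is at Month 12. Footnote k puts the scan early: "Screening MRI will be performed after informed consent form has been signed and prior to other screening assessments". Footnote a gives its window: "Screening MRI and ocular assessments may be performed up to 6 weeks prior to Day 1". Randomisation and first dispensing are both marked on Day 1.

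**Analysis.** Under Protocol 9.5, members of the Efficacy Population must "have a centrally read MRI at baseline and after 12 months of treatment". SAP 3.3 uses the same requirement and adds: "This will be the primary population for efficacy analyses". In the primary ANCOVA (SAP 3.9.2), baseline log10 htTKV is part of the outcome and is also the covariate. Under SAP 3.2.3, a parameter with no pre-dose value has a missing baseline, and SAP 3.2.4 generally rules out imputation.

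**The concern.** Entry rests on one reading of the scan and the primary analysis on another, and nothing links the two before the subject is randomised. If the central reader finds the screening scan unusable after dosing has begun, it cannot be replaced, because any later scan is taken on treatment. The subject then has no change from baseline in htTKV at any visit.

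Running the ANCOVA on the mITT population, as SAP 3.10 plans, does not recover the subject, because that model also needs the baseline. The eGFR ANCOVA in SAP 3.9.3 is affected too, since it includes baseline htTKV as a covariate.

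Two things are at stake: a little precision, and up to 24 months of study treatment for someone who cannot contribute to the primary comparison. The protocol does use central confirmation at entry elsewhere. Screening QTcF must meet its limit by central analysis (Section 7.5, Electrocardiogram), and laboratory eligibility uses central laboratory results (Section 7.5, Clinical Laboratory Evaluations).

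**Working it through.** **Inputs from the documents** (Protocol 9.12, SAP 3.1.2): mean 12-month change 83.6 mL on placebo and 26.4 mL on tesevatinib; SD 90.0 mL, taken as common to both arms; two-sided alpha 0.05; 40 analysable per arm; 50 randomised per arm.

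**Input not in the documents:** u, the proportion of randomised subjects whose baseline scan is adequate locally but not centrally. I assume 1% to 5%.

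**Step 1: reproduce the plan's power.** The difference is 83.6 − 26.4 = 57.2 mL. For a two-sample t-test with n per arm, the noncentrality is 57.2 / (90 × √(2/n)) on 2n − 2 degrees of freedom. At n = 40 it is 57.2 / 20.12 = 2.84, the critical value is 1.991, and power is 80.2%. This agrees with the stated figure of about 80%.

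**Step 2: the allowance.** 40 / 50 = 0.80, so the ten extra subjects per arm cover a 20% loss. The plan assigns them to drop-outs and differences in analysis method; unreadable baselines are not named.

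**Step 3: add the loss.** Suppose the 20% is otherwise fully used. Analysable subjects per arm are then 50 × 0.80 × (1 − u):

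| Assumed u | Expected affected of 100 | Analysable per arm | Power | Chance of at least one, 1 − (1 − u)^100 |
|---|---|---|---|---|
| 0 | 0 | 40.0 | 80.2% | 0% |
| 1% | 1 | 39.6 | 79.8% | 63% |
| 2% | 2 | 39.2 | 79.3% | 87% |
| 3% | 3 | 38.8 | 78.9% | 95% |
| 5% | 5 | 38.0 | 78.1% | 99% |

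The loss is 0.4 to 2.1 percentage points.

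**Step 4: relax the assumption in Step 3.** The 40 per arm in the synopsis are those expected to finish all study procedures, which run past Month 24. The primary endpoint is at Month 12, so more than 40 per arm may be analysable then. The same formula gives 82.1% at 42 per arm and 84.7% at 45. Step 3 is therefore the pessimistic case.

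**Step 5: compare the two baseline windows.** Table 2 footnote a allows the screening MRI up to 6 weeks (42 days) before Day 1. SAP 3.2.3 takes baseline from the 28 days before first dose unless the relevant assessment section says otherwise, and SAP 2.4.1 on htTKV makes no exception. Read literally, a perfectly readable scan from Day −42 to Day −29 is also a missing baseline. Any fix that uses the 42-day window has to deal with this.

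**The case against.** The case for leaving the plan as it is has real strength.

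- **A partial safeguard exists.** Inclusion criterion 5 requires an htTKV calculated from MRI, so a scan that is absent or grossly unusable should already fail at entry. This stands. Only a scan good enough locally but not centrally remains at risk.
- **The subject is not wasted.** Safety data still count. The mixed model in SAP 3.10.1 treats baseline as one of the responses, so later scans can be used, and SAP 3.9 assigns supplemental analyses to the mITT population. This stands, but the model is supplementary and does not restore the primary analysis.
- **A repeat scan is not forbidden, and 24 months is a maximum.** Both are true. But nothing in the documents triggers a repeat scan before the first dose.
- **Local entry with central reading is a deliberate choice.** It is, and it can stay: readability can be checked without moving eligibility to the central value.

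Three stronger readings are tempting, and the documents do not support them.

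- A reader might infer from a table footnote in the Protocol's account of Study KD019-101, "One subject did not have a baseline TKV value", that central readings have already failed in this programme, and might take a rate from it. The footnote gives no reason. The scan may not have been done, or the value not recorded. It supplies no rate for this event.
- A reader might infer that the trial cannot absorb any such loss, because 40 is the smallest number per arm reaching 80% power. But 50 per arm are randomised, and Step 4 shows that there may be room at Month 12.
- A reader might infer bias. The scan precedes randomisation, so treatment cannot affect its readability.

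**Conclusion.** The gap is real. The documents let a subject be randomised and treated for up to 24 months with a baseline scan that the primary htTKV analysis cannot use, and no check is in place to prevent this. The consequence is small: at assumed rates of 1% to 5%, power falls from 80.2% to between 79.8% and 78.1%. Those figures rest on an assumed rate, on the plan's own difference and SD, and on the 20% allowance being otherwise exhausted. The loss costs precision and the subject's contribution to the primary comparison; it does not bias that comparison. This is an optional improvement, worth making because it is cheap. The 28-day and 42-day baseline windows should be reconciled whether or not the check is adopted.

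**What to change.** 1. Add to Protocol 7.4 and the IVRS/IWRS specification that a randomisation number is released only after the central reader confirms that the screening MRI is evaluable for htTKV. Eligibility may still rest on the local value.
2. State that a scan judged not evaluable is repeated before Day 1, within the screening MRI window.
3. Amend SAP 3.2.3 (or add the exception in SAP 2.4.1) so that the htTKV baseline accepts the screening MRI from up to 42 days before first dose. Without this, waiting for the central reader could push some readable scans outside the 28-day rule.

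**Cost:** short additions to the protocol, the IVRS/IWRS specification and the SAP. The central baseline reading is already planned, and the MRI comes first in screening, so the check can run while other assessments are completed. The downside is some central turnaround time before randomisation, whose length the documents do not give, and an occasional repeat scan.
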